Busulfan crosses the blood-brain barrier and can cause neurotoxicity, including seizures, when administered at higher doses. Therefore, anticonvulsant medication is routinely prescribed for patients undergoing myeloablative therapy with busulfan in preparation for bone marrow transplant (BMT) or hematopoietic cell transplant (HCT). Consistent with this practice, anticonvulsant prophylaxis will be administered concurrent with busulfan administration for conditioning in this study. Levetiracetam will be administered in this study as described in Section 8.1.1.3. The dosing regimen selected for levetiracetam has been shown in literature to be effective at preventing seizures in adults receiving conditioning with busulfan in preparation for HSCT, and to have an acceptable safety profile when administered in combination with busulfan (Akiyama 2018). For subjects with contraindications to levetiracetam, an alternative anti-

convulsant medication (eg, benzodiazepines or valproic acid) may be used before and after busulfan treatment (Busulfan PI).

Busulfan treatment at the approved dose and schedule produces profound, transient myelosuppression in all patients. Hematologic changes have been observed in subjects receiving myeloablative busulfan conditioning regimens used in other autologous LV-mediated gene therapy studies for TDT, sickle cell disease (SCD), metachromatic leukodystrophy (MLD), leukocytes adhesion deficiency-1, and X-linked chronic granulomatous disease (Fumagalli 2022; Sessa 2016; Thompson 2018; Tisdale 2018; Kohn 2020; see also the Investigator's Brochure for AVR-RD-02). Similar outcomes were achieved by Mamcarz et al in LV-mediated gene therapy for X-linked severe combined immunodeficiency (SCID-X1) patients, albeit targeted busulfan was indicated at low dose (Mamcarz 2019).

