 - a. For male subjects and for male spouses/partners of female subjects, condoms are an acceptable method of barrier contraception.
 - b. For female subjects and for female spouses/partners of male subjects, acceptable methods of barrier contraception include diaphragm, cervical cap, or contraceptive sponge.

- 7. Male and female subjects must agree to refrain from donating sperm and eggs, respectively, after undergoing conditioning.
- 8. Subject must be willing to refrain from donating blood, organs, tissues, or cells for gene therapy infusion any time after AVR-RD-02 treatment.
- 9. Subject must be willing to receive blood or blood products transfusion to manage AEs.

Additional Inclusion Criteria for Switch-stable Subjects:

In addition to inclusion criteria 1 through 9, switch-stable subjects must meet all of the following inclusion criteria for participation in this study:

- 10. Subject has undergone a stable dose (within 75% to 125% of the prescribed dose) of ERT ≥ 15 U/kg and ≤ 60 U/kg every other week (or equivalent; ie, any combination of infusions resulting in a total monthly ERT dose of ≥ 30 U/kg and ≤ 120 U/kg) for ≥ 24 consecutive months with no significant interruptions, in the opinion of the Investigator, in dosing over the last 6 months prior to Screening.
- 11. Subject has normal or near-normal hematologic values at Screening defined as one or more of the following:
 - a. Hemoglobin concentration $\geq 10g/dL$
 - b. Platelet count $\geq 80 \times 109/L$
- 12. Subject has stable Gaucher disease during the 6 months immediately preceding Screening defined by:
 - a. Stable hemoglobin concentration (ie, within a range of \pm 2 g/dL of the Screening value) based on documented historical clinical laboratory results

and

Stable platelet count (within \pm 20% of the Screening value) based on documented historical clinical laboratory results

13. Subject has not received SRT for Gaucher disease during the 12 months immediately preceding Screening.

Additional Inclusion Criteria for Treatment-naïve Subjects:

In addition to inclusion criteria 1 through 9, treatment-naïve subjects must meet the following inclusion criteria for participation in this study:

- 14. Subject has never received either ERT or SRT for Gaucher disease or has not received either ERT or SRT for Gaucher disease within 12 months of Screening.

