7.2 Exclusion Criteria

Subjects will be excluded from participation in this study if they meet any of the following exclusion criteria:

- 1. Subject has Type 2 or 3 Gaucher disease, has severe neurological signs and symptoms, defined as complete ocular paralysis, overt myoclonus or history of seizures, characteristic of neuronopathic Gaucher disease, or has a tremor, peripheral neuropathy or symptoms of Parkinson's disease.
- 2. Subject has any one of the following:
 - a. Hemoglobin value < 9.0 g/dL, or
 - b. Platelet count $< 70 \times 10^9/L$, or
 - c. Spleen volume $> 10 \times \text{normal}$, or
 - d. Pulmonary hypertension
- 3. Subject has experienced a prior anaphylactic or anaphylactoid reaction (of any severity) to ERT.
- 4. Treatment-naïve subject has history of clinically significant (CS) anti-GCase antibodies.
- 5. Subject has a contraindication to ERT, in the opinion of the Investigator.
- 6. Subject has a contraindication to HSC transplantation, in the opinion of the Investigator.
- 7. Subject presents with iron, folic acid, and/or vitamin B12 deficiency sustained anemia during Screening.
- 8. Subject has idiopathic thrombocytopenic purpura (ITP), thrombotic thrombocytopenic purpura (TTP), thrombocytopenia, anemia, hepatomegaly, splenomegaly, and/or osteoporosis unrelated to Gaucher disease, in the opinion of the Investigator.
- 9. Subject has a clinical co-morbidity such as neurologic, cardiovascular, pulmonary, hepatic, gastrointestinal, renal, hematologic, endocrine, metabolic, genetic, immunologic, neoplastic, or psychiatric disease, other medical condition(s), or intercurrent illnesses that may confound the study results or, in the opinion of the Investigator, may preclude participation in the study.
- 10. Subject is a pregnant and/or lactating female.
- 11. Subject is unable to understand the nature, scope, and possible consequences of the study.
- 12. Subject has diabetes mellitus (Type 1 or Type 2).
- 13. Subject has active, progressive bone necrosis.
- 14. Subject has an active chronic infection during the Screening, Baseline, or Pre-gene Therapy Infusion Period of the study.
- 15. Subject has an active uncontrolled acute bacterial, viral, fungal, parasitic, or prion-associated infection during the Screening, Baseline, or Pre-gene Therapy Infusion Period of the study.
- 16. Subject has a history of (or current) tuberculosis.

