11.8.2 Clinical Laboratory Tests

All individual clinical laboratory results will be presented in data listings. Values outside the laboratory reference range will be flagged (low-L, high-H).

Observed values and changes from Baseline in clinical laboratory data will be summarized at each protocol-scheduled time point. Frequency tabulations of the number of normal and abnormal (low and high) records, as well as the number of CS and not clinically significant (NCS) records, will also be summarized at each protocol-scheduled time point. Urinalysis results will be summarized at each protocol-scheduled time point using frequency tabulations, and any available microscopic urinalysis results will be listed.

In addition, shift tables will be produced per CTCAE grading.

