10.1.3. Clinical Laboratory Evaluations

The details of measurement of laboratory parameters are described in the study protocol. International System (SI) units will be used in all outputs.

Serum chemistry includes aspartate aminotransferase (AST), alanine aminotransferase (ALT), gamma-glutamyl transferase (GGT), amylase, lipase, alkaline phosphatase (ALP), lactate dehydrogenase (LDH), bilirubin, calcium, albumin, phosphate, magnesium, uric acid, and glucose.

Electrolytes include sodium, potassium, chloride, bicarbonate, blood urea nitrogen (BUN), and serum creatinine.

Hematology includes hematocrit, hemoglobin, platelet count, WBC count (total and differential), RBC count, and ANC.

All hematology, serum chemistry and urinalysis data including CFB will be listed. In these listings, sample collection data (e.g., collection times) for laboratory analysis and urinalysis data will be included, and individual data will be flagged with an "H" or an "L" for values that are higher or lower than their normal ranges, respectively, and any clinically significant (CS) and not clinically significant (NCS) records will be flagged.

For the listings of ALT and of AST, the following values will be flagged to indicate evidence of Drug-Induced Liver Injury:

- ALT or AST $> 8 \times ULN$
- ALT or AST $> 5 \times ULN$
 - In the CSR, an assessment will be made of whether ALT or AST remained above 5×ULN for more than 2 weeks
- ALT or AST $> 3 \times ULN$

 In the CSR, an assessment will be made of whether ALT or AST remained above 3×ULN with the appearance of fatigue, nausea, vomiting, right upper quadrant pain or tenderness, fever, rash, and/or eosinophilia (>5%)

For the listing of ANC values, a flag will indicate ANC $< 0.5 (10^9/L)$.

For the listing of platelet values, flags will indicate platelets $< 35 (10^{9}/L)$ and $< 20 (10^{9}/L)$.

For each laboratory parameter with a defined normal range, absolute values will be defined at each protocol-scheduled time point as low, normal, or high, and post-baseline values will be compared to the baseline value through shift tables.

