In addition, one flag will be derived to identify whether the parameter had at least one value above the normal range at any time post-treatment, and another to identify whether the parameter had at least one value below the normal range at any time post-treatment. Subjects having both High and Low values relative to normal ranges at post-treatment visits for laboratory parameters will be counted in both the High and Low categories of the "Any visit post-treatment" row of related summary tables.

The denominator used in laboratory shift table summaries will only include evaluable subjects (i.e., those who have both a baseline and at least one post-baseline value recorded).

Individual subject data for the ratio of value to LLN for Hgb, HCT, ANC, Platelets, Reticulocytes and Leukocytes will be plotted vs. study week, with a line for each parameter on the same plot and one plot for each subject. Vertical reference lines will be included to represent the study day the subjects received their AVR-RD-02 infusion and their first and last doses of busulfan. A horizontal reference line will be included at 1.

Any available microscopic urinalysis will also be listed.

Partial thromboplastin time (PTT) and international normalized ratio (INR) will be listed.

Flow cytometric analysis of T and B cell counts as well as peripheral blood lymphocyte subsets (CD3, CD4, CD8, CD19, and CD16/56) will be listed.

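### SAP laboratory shift tables use low/normal/high where the protocol plans CTCAE grades, so worsening from an already abnormal Baseline shows as no shift

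*SAP*

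**What the plan says.** Protocol 11.8.2 plans frequency tables of normal and abnormal (low, high) laboratory records, and then adds a second display: "In addition, shift tables will be produced per CTCAE grading".

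SAP 10.1.3 keeps shift tables but changes their scale. For each parameter with a normal range, "absolute values will be defined at each protocol-scheduled time point as low, normal, or high". The comparison with Baseline is then made on those three categories, again by shift table. Two further flags feed a row covering any post-treatment visit. One marks a value above the normal range, and "another to identify whether the parameter had at least one value below the normal range at any time post-treatment". That row is therefore on the same scale.

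SAP section 1 states that the SAP supersedes the protocol on analysis. SAP 10.4 names two changes, the abbreviated CSR and the replaced analysis sets, and not this one. Elsewhere the SAP uses CTCAE for adverse events (10.1.1.5, v4.03) and in the medical history listing (8.4), but never to grade laboratory values for a shift table.

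**The concern.** Change from Baseline in safety laboratory values is a primary safety endpoint (Protocol 5.2.1, SAP 2.2.2.1). A shift table should show who worsened relative to where they started. A three-category table cannot show movement within a category, and in this trial that movement is expected.

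Subjects can start below normal. Inclusion criterion 11 reads "Subject has normal or near-normal hematologic values at Screening defined as one or more of the following", followed by hemoglobin of at least 10 g/dL and platelets of at least 80 ×10⁹/L. Exclusion criterion 2 sets the floor: it opens with "Hemoglobin value < 9.0 g/dL, or" and continues with platelets below 70 ×10⁹/L. Deep falls are also expected. Protocol 6.2.2.2 says that busulfan at the approved dose and schedule "produces profound, transient myelosuppression in all patients".

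At stake is whether the laboratory tables can separate a mild from a severe fall, and whether they can show a return to the Baseline grade.

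**Working it through.** No figure in the plan depends on this point: there are no hypothesis tests, and the sample size was set without statistical considerations. The check applies the SAP rule to Baseline values that eligibility permits, then looks at what the other outputs cover.

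**1. The rule.** A value is Low if it is below the lower limit of normal (LLN), High if above the upper limit, and otherwise Normal. A shift is recorded only if the Baseline and later categories differ. If Baseline < LLN and the later value < Baseline, the later value is also < LLN. The cell is then Low to Low for any size of fall. The mirror argument applies to a subject who is High at Baseline and rises further, for example in ALT.

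**2. Inputs.** Platelet Baselines of 70, 80 and 95 ×10⁹/L and hemoglobin Baselines of 9.0, 10.0 and 11.0 g/dL are compatible with the criteria above. A Baseline at 70 needs hemoglobin of at least 10, and one at 9.0 needs platelets of at least 80. Later values lie around the documents' own thresholds (platelets 35 and 20 ×10⁹/L, hemoglobin 7.0 g/dL). The documents give no LLN for either parameter, so it is assumed over a range.

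**3. Results.**

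| Parameter | Baseline | Later value | Assumed LLN | Combinations | Result |
|---|---|---|---|---|---|
| Platelets (×10⁹/L) | 70, 80, 95 | 60, 34, 19, 5 | 100, 120, 150 | 3 × 4 × 3 = 36 | all Low to Low |
| Hemoglobin (g/dL) | 9.0; 10.0; 11.0 | 6.9; 6.9; 7.5 | 11.5, 12.0, 13.5 | 3 × 3 = 9 | all Low to Low |

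The deepest platelet falls leave 5/95 = 5% to 5/70 = 7% of Baseline. A fall from 70 to 60 (60/70 = 86%) lands in the same cell.

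**4. The any-visit row.** A subject who is Normal at Baseline does show a shift to Low, but without depth. With profound myelosuppression expected in all patients, this row should be Low for nearly every subject for ANC, WBC and platelets. That is an expectation from the protocol's statement, not a calculated rate.

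**5. What else covers severity.**

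| Parameter | Automatic AE by CTCAE grade (Protocol 9.2.1, SAP 10.1.1) | Other SAP outputs |
|---|---|---|
| Platelets | Grade 3 or higher | Flags below 35 and 20 ×10⁹/L and below 80% of Baseline; subject plots |
| WBC | Grade 3 or higher | Ratio-to-LLN subject plots |
| ANC | Grade 2 or higher | Flag below 0.5 ×10⁹/L; subject plots |
| Hemoglobin | None | Flags for a fall above 2 g/dL and below 80% of Baseline; figures; ratio-to-LLN subject plots |
| ALT, AST | None | Flags above 3, 5 and 8 × ULN |
| Other chemistry, electrolytes | None | High/low and clinical-significance flags in listings |

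Parameters without an automatic AE become one only if the investigator judges the worsening clinically significant (Protocol 9.1.3). The dedicated ANC and platelet panels end at study day 100 (SAP, Achievement of Hematological Engraftment). The ratio-to-LLN plots state no such limit. None of these outputs tabulates Baseline grade against later grade.

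**The case against.** The strongest reply is that the report does show severity. Grade 3 platelet and WBC counts and Grade 2 neutrophil counts are adverse events whether or not the investigator thinks them significant, and they are tabulated by each CTCAE grade. Listings give every value with its change from Baseline. The hemoglobin and platelet figures relative to Baseline, with a line at 0.8, show recovery to the subject's own starting value more finely than a grade would. This stands. A reader might infer that severe cytopenia is hidden from the report, or that recovery cannot be seen; the documents do not support either inference.

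Nor is it established that the shift tables are the only tabulated laboratory summary. SAP 5.4 sets general summary statistics for safety data and changes from Baseline, including the minimum, although 10.1.3 does not repeat them.

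On documentation, Protocol 11.1 lets the SAP modify the statistical sections and assigns the justification to the CSR. SAP 10.4 likewise promises a summary of changes in the study report. The departure is therefore permitted. What remains is that 10.4 names other changes and omits this one, and that an abbreviated CSR does not explain it, because shift tables are retained and only their scale is coarsened.

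It is also fair that the trial is small (about 8 to 16 planned), was stopped early and has only switch-stable subjects. How many of them start outside the normal range is not known from the documents. Finally, worst post-baseline grade for ANC, WBC and platelets may cluster at the top grades. That is why a by-visit grade table is needed beside it.

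**Conclusion.** The point holds in a limited form. The SAP replaces a display planned in the protocol for a primary safety endpoint with a coarser one and does not record the change. Within those tables, any worsening from an already Low or High Baseline is shown as no shift, whatever its size. This follows from the rule itself; the assumed LLN decides only which Baselines count as Low. It also assumes that Baseline values resemble those allowed at Screening.

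The loss is confined to the tables. It matters least for platelets, WBC and ANC, where graded adverse events fill most of the gap. It matters more for hemoglobin, which has flags, figures and investigator-judged events but no automatic event by grade. It matters most for chemistry other than ALT/AST, which has listing flags and investigator-judged events only. For every parameter, the Baseline-grade by later-grade comparison is missing.

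**What to change.** In SAP 10.1.3, restore the protocol's shift tables for every parameter that CTCAE v4.03 grades: Baseline grade against grade at each scheduled visit, and Baseline grade against worst post-baseline grade. Keep low/normal/high for parameters without a grade. The protocol asks only for shift tables by grade; this two-part layout is a proposal, chosen so that both depth and recovery can be read. Record any remaining departure from Protocol 11.8.2 in SAP 10.4 and justify it in the CSR.

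The cost is a small amount of extra programming. Shift tables are already planned, v4.03 is already the grading system for adverse events, and no new data are needed.

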10.1.1. Achievement of Hematological Engraftment

The occurrence of hematological reconstitution is defined as the first day of absolute neutrophil count (ANC) $\ge 0.5 (10^9/L)$ and of platelets $\ge 20 (10^9/L)$ (in the absence of platelet transfusions), i.e. time (days) from date of AVR-RD-02 infusion to the first date of the three consecutive values.

For the Infused Population, panel plots of individual subjects will be presented for ANC $(10^9/L)$ between study day -50 and study day 100, with study day on the x-axis. Vertical reference lines will be included at study day 1 (solid, black), 35 (dashed, red), 42 (solid, red) and 49 (dashed, red) and to represent the study day the subjects received their AVR-RD-02 infusion and their first and last doses of busulfan. A horizontal reference line will be included at 0.5 ($10^9/L$). On the x-axis, red arrows will indicate the study days that G-CSF was administered.

For the Infused Population, panel plots of individual subjects will be presented for platelet counts $(10^9/L)$ between study day -50 and study day 100, with study day on the x-axis. Vertical reference lines will be included at study day 1 (solid, black), 35 (dashed, red), 42 (solid, red) and

49 (dashed, red) and to represent the study day the subjects received their AVR-RD-02 infusion and their first and last doses of busulfan. Horizontal reference lines will be included at 20 and 35 $(10^9/L)$. On the x-axis, red arrows will indicate the study days that any platelet transfusions were administered.

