6.2.3 Efficacy and Safety Measures

Measures of engraftment of gene-augmented HSCs will be evaluated by determining average VCN using qPCR and/or ddPCR in peripheral blood and bone marrow. To ensure subject safety, a CD34+ stem cell back-up of nontransduced cells will be collected and stored for use as rescue treatment in the unlikely event that there is prolonged bone marrow aplasia after AVR-RD-02 treatment (see Section 8.1.1.1).

Efficacy measures chosen for the planned AVRO-RD-02-201 study have been commonly used to measure treatment effects in trials of ERT and SRT for Gaucher disease. Efficacy and safety endpoints chosen, and the timing of these assessments, considered the following: the natural history of Gaucher disease, the clinical progression of signs/symptoms known to impact morbidity and mortality in subjects with the disease, and regulatory guidelines for follow-up of subjects receiving gene therapy products (ie, US Department of Health and Human Services [DHHS], FDA, Center for Biologics Evaluation and Research [CBER], Guidance for Industry, Long Term Follow-Up After Administration of Human Gene Therapy Products, January 2020 [FDA 2020a] US DHHS, FDA, CBER, Guidance for Industry, Testing of Retroviral Vector-Based Human Gene Therapy Products for Replication Competent Retrovirus During Product Manufacture and Patient Follow-up, January 2020 [FDA 2020b] EMA, Guideline on Follow-up of Patients Administered with Gene Therapy Medicinal Products, October 2009 [EMA 2009]).

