7.4.4.2 Enrollment Pause Criteria

- Enrollment in this study may be paused at any time for safety reasons.
- In the event enrollment is paused, subjects who have already been treated with AVR-RD-02 Drug Product will continue in the study.
- The following are examples of events that may result in enrollment pause.
 - Death of a subject that is attributed as possibly, probably, or definitely related to AVR-RD-02.
 - Leukemia/lymphoma that is attributed to an AVRO-RD-02-201 study procedure.
 - Any individual subject shows no or sub-optimal evidence of engraftment of AVR-RD-02 gene modified cells (based on average VCN in blood and bone marrow samples or GCase enzyme activity in blood) at or after Week 26 assessments.
 - Detection of leukemia/lymphoma due to vector-mediated oncogenesis by insertional mutagenesis.
 - Failure to achieve reconstitution with transduced cells in at least one subject, necessitating the use of rescue cells.
 - Unexpected, CS, AVRO-RD-02-related Grade 3 or Grade 4 toxicities in > 2 subjects.
- If enrollment pause occurs, gene therapy infusion procedures in additional subjects will be temporarily paused, and a safety review meeting will take place with the DMC and the Sponsor.
- A determination will be made as to whether the trial should continue without change, continue with specific changes, or terminate.
- The Sponsor will inform the regulatory authorities and the Investigators, and each site's IRB/IEC and other appropriate institutional regulatory bodies will be promptly notified if a decision to pause enrollment is made.

Study enrollment may resume if appropriate changes to study conduct are identified and implemented to reduce any risks to subjects going forward.

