7.4.5 Engraftment Failure

Engraftment failure is defined as failure to achieve an absolute neutrophil count (ANC) $\geq 0.5 \times 10^9 / L$ by Day 42 post-gene therapy infusion of AVR-RD-02 Drug Product. In the event of an engraftment failure:

- The subject should receive the back-up rescue cells.
- Based on the Investigator's discretion, the subject may receive additional evaluations and/or treatments that are outside the scope of this protocol to monitor for and manage engraftment failure.

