10.1.2. Rescue Medication

To ensure subject safety, a CD34+ stem cell back-up of non-transduced cells will be collected and stored for use as rescue treatment in the unlikely event that there is prolonged bone marrow aplasia after AVR-RD-02 treatment.

Any such cases of rescue treatment will be listed.

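### The SAP's hematological reconstitution rule excludes platelet transfusions but not rescue cells, so recovery on untransduced back-up cells would be dated as recovery on AVR-RD-02

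*SAP*

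**What the plan says.** The rule is in the SAP section headed "Achievement of Hematological Engraftment". That section is numbered 10.1.1, a number the SAP uses more than once. It begins "The occurrence of hematological reconstitution is defined as the first day of absolute neutrophil count (ANC", sets thresholds of ANC at least 0.5 and platelets at least 20 (10^9/L), and finishes with the only exclusion and the time origin: "in the absence of platelet transfusions), i.e. time (days) from date of AVR-RD-02 infusion to the first date of the three consecutive values". It sets no latest day and does not mention rescue cells.

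The same section specifies individual ANC and platelet panel plots from study day -50 to 100 for the Infused population. Red arrows mark G-CSF days on the ANC plot and platelet transfusion days on the platelet plot.

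On rescue, SAP 10.1.2 (Rescue Medication) says only "Any such cases of rescue treatment will be listed".

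The protocol treats the same event as a failure:

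- Section 7.4.5: "Engraftment failure is defined as failure to achieve an absolute neutrophil count (ANC" at or above 0.5 × 10^9/L by Day 42. The first consequence is "The subject should receive the back-up rescue cells".
- Section 6.2.3, on what those cells are: "a CD34+ stem cell back-up of nontransduced cells will be collected and stored for use as rescue treatment".
- Section 7.4.4.2, among examples of events that may pause enrollment: "Failure to achieve reconstitution with transduced cells in at least one subject, necessitating the use of rescue cells".

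**The concern.** The SAP rule is meant to say whether, and when, a subject's counts recovered after myeloablation and AVR-RD-02. It already recognises that a count supplied from outside the graft should not qualify, since platelets supported by transfusion are excluded. A second, untransduced graft is a much larger outside source, and it is neither excluded from the rule nor marked on the plots.

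The SAP states in its introduction that it supersedes the protocol on analysis specifications, and it does not carry over the protocol's engraftment-failure definition. One subject could therefore be an engraftment failure under protocol 7.4.5 and have a reconstitution date, counted from AVR-RD-02 infusion, under the SAP. In a first-in-human study of a myeloablative procedure, whether marrow recovered on the product alone is a safety question. The derived variable should not answer it wrongly in the very case the protocol singles out.

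**Working it through.** The plan gives no figure to reproduce. The sample size of 8 to 16 was chosen without statistical considerations, and no tests are planned. The check is to write the rule out and apply it.

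**Inputs from the documents**

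- Thresholds, three consecutive values, platelet-transfusion exclusion and time origin: SAP 10.1.1.
- Failure if ANC 0.5 is not reached by Day 42, followed by back-up cells: protocol 7.4.5.
- Back-up cells are untransduced: protocol 6.2.3 and SAP 10.1.2.
- A rescued subject stays in the analysis, because the Infused population (SAP 5.5.3) requires only the auxiliary medications and AVR-RD-02.

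**The rule as a formula.** Let t be days from AVR-RD-02 infusion.

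- As written: T = the first t at which that value and the next two all have ANC ≥ 0.5 and platelets ≥ 20, with no platelet transfusion.
- With a rescue condition: T as above if reached before any rescue cells; otherwise not achieved on AVR-RD-02.

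**Assumptions for illustration** (none is in the documents): daily counts from Day 7 to Day 100; ANC 0.1 and platelets 10 before recovery, 0.9 and 40 from recovery onward; no platelet transfusion; rescue cells on Day 43 where rescue is given.

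| Subject | Protocol 7.4.5 status | SAP rule as written | With rescue condition |
|---|---|---|---|
| Rescue Day 43, recovers Day 50 | failure | Day 50 | not achieved |
| Rescue Day 43, recovers Day 57 | failure | Day 57 | not achieved |
| Rescue Day 43, recovers Day 64 | failure | Day 64 | not achieved |
| Rescue Day 43, recovers Day 75 | failure | Day 75 | not achieved |
| No rescue, recovers Day 18 | not failure | Day 18 | Day 18 |
| No rescue, recovers Day 44 | failure | Day 44 | Day 44 |

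The first five rows were run; the sixth follows directly from the two formulas. The SAP sentence could mean the two cell lines jointly or separately. In these examples both cross on the same day, so the dates are the same either way, and neither reading introduces a rescue condition.

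All four rescued recoveries fall inside the plotted range, which ends at study day 100. No symbol on either plot would show that a second graft came between infusion and recovery.

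**The case against.** The strongest reply is that little depends on this variable, and much of that reply stands.

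- **Primary engraftment is measured elsewhere.** The primary engraftment endpoint is vector copy number in blood and marrow (SAP 2.2.1.1 and 9.2). Rescue cells carry no vector, so that endpoint does not inherit the error. A reader might infer that rescue could make the product look engrafted whatever it does; the documents do not support that.
- **No rate is planned.** The section specifies individual plots, with no proportion, summary table or time-to-event estimate. A reader might infer that the report will show an inflated reconstitution rate, but the SAP plans no such output. Any percentage would also need assumed rates of product engraftment and rescue success, which the documents do not give.
- **The case can be found by eye.** The ANC plot has a line at 0.5 and a vertical line at study day 42, the laboratory listing flags ANC below 0.5, and rescue cases are listed. This limits the harm but does not correct the derived status and date. The line classifies nobody. The SAP also counts infusion as study day 1 while the protocol counts it as Day 0, so the line falls on protocol Day 41 (42 − 1).
- **Rescue may never have happened.** Both documents call it unlikely, and the study was stopped early. If nobody was rescued, no result changes.

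One might also say that the SAP term means count recovery from any source. The section heading, the AVR-RD-02 time origin and the platelet-transfusion exclusion all point the other way.

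**Conclusion.** The point holds, within narrow limits. As written, the rule gives a wrong derived status and time for a subject who fails to engraft, receives untransduced back-up cells and then recovers. The two panel plots leave the reason for recovery unmarked. This is a stated rule giving the wrong answer, and nothing else in the SAP corrects it.

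The size is one subject's status and date per rescue. If someone chose to compute a proportion, which the SAP does not plan, one rescued subject with all others engrafting would give 8/8 (100%) against 7/8 (87.5%), or 16/16 (100%) against 15/16 (93.75%), at the planned sizes.

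It might seem to follow that every subject who passes Day 42 without recovery should lose a reconstitution time. It does not. A subject who recovers late on AVR-RD-02 alone has a genuine recovery time, as the Day 44 row shows; only rescue makes the source of recovery uncertain.

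The conclusion rests on the literal text of the rule and on no assumed rate. The consequence is conditional, because the documents do not say that any subject received rescue cells.

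**What to change.** In the SAP section on achievement of hematological engraftment:

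1. Add that the qualifying values must occur before any rescue cells.
2. Report a rescued subject who had not already met the rule as 'not achieved on AVR-RD-02', and show any later recovery separately as 'recovery after rescue cells'.
3. Report the protocol 7.4.5 Day 42 failure status as a separate item, and keep the observed recovery time for a subject who recovers late without rescue.
4. Mark the rescue-cell date on both panel plots and name it as a field in the rescue listing, which at present specifies no fields.

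The cost is one more condition in the derivation, a marker on two plots and a date field, with a possibly less favourable result for any rescued subject. Subjects without rescue keep the time they have now. The change affects the analysis only and leaves the clinical handling of engraftment failure as it is.
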